5.7 Vital Signs and Weight

For the safety population, descriptive statistics of vital signs and weight will be presented at pre-injection and post-injection time points for pulse, systolic BP, diastolic BP,

temperature, and respiratory rate as well as body weight for Treatment Session 1, Treatment Session 2, Treatment Session 3 and for Treatment Session 4.

5.8 Neurologic Exam

For the safety population, abnormal findings of neurological exam data will be listed, respectively, for individual subjects.

5.9 Lung Functioning Test

For the safety population, findings of forced vital capacity (FVC) data will be listed, respectively, for individual subjects.

5.10 Physical Examination

Clinically abnormal findings from the physical examinations are either reported with the medical history if they occurred prior to 1st injection or as adverse events if findings are after first injection.

5.11 Clinical Laboratory Evaluation

For the safety population, descriptive statistics of clinical laboratory tests will be presented at screening and end of treatment session respectively, for hematology, chemistry, and urinalysis (specific gravity and pH) for Treatment Session 1, Treatment Session 2, Treatment Session 4 as well as End of Study. Qualitative findings in terms of abnormal low, normal, and abnormal high at screening and end of treatment session will be tabulated for hematology, chemistry, and urinalysis, respectively, for Treatment Session 1, Treatment Session 2, Treatment Session 4 as well as End of Study.

Any clinically significant abnormalities (based upon laboratory ranges) observed during the study will be listed for hematology, chemistry, and urinalysis, as well as pregnancy test.

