16.4 Clinical Laboratory Evaluations

16.4.1 Standard Laboratory Tests

Safety blood and urine specimens (fasting) (see Table 3) will be collected from all subjects at screening and Weeks 13, 26, and 52 or, if applicable, at discontinuation from the study. Clinical laboratory testing will also be performed as needed at the Investigator's discretion throughout the study. For this multicenter study, a central laboratory (TBD) will be used that is directly accredited by the College of American Pathologists (CAP) and licensed by the Clinical Laboratory Improvement Act of 1988 (CLIA); both certification and accreditation must be renewed every 2 years. The laboratory will need to provide a copy of current certification and provide the Laboratory Normals for their laboratory values to determine the upper limit of normal (ULN).

Table 3. Hematology, Chemistry and Urinalysis Tests

Hematology	Chemistry	Urinalysis
Hemoglobin	Cholesterol	Specific gravity
Hematocrit	Phosphorus	pH
Platelet count	Sodium	Glucose
Red blood cell count	Potassium	Blood
MCV	Calcium	Protein
MCH	Urea nitrogen	Color
MCHC	Creatinine	Nitrites
WBC count	Albumin	Ketones
WBC differential (%)	Total protein	Bilirubin
bands	Aspartate aminotransferase	Urobilinogen
neutrophils	Alanine aminotransferase	Leukocyte esterase
lymphocytes	Alkaline phosphatase	
monocytes	Gamma-glutamyl transferase	
eosinophils	Uric acid	
basophils	Total bilirubin	
	Glucose	
	Lactate dehydrogenase	

Abbreviations: MCH = mean corpuscular hemoglobin, MCHC = mean corpuscular hemoglobin concentration, MCV = mean corpuscular volume, WBC = white blood cell

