For the analysis, an intensity of suicidal ideation will be defined as the maximum suicidal ideation category (1-5 on the C-SSRS) present at the assessment. A score of 0 will be assigned if no ideation is present.

Clinical laboratory tests are conducted at screening, Weeks 13, 26, as needed at the Investigator's discretion throughout the study and at study completion (i.e., Week 52) or, if applicable, at early termination from the study. Laboratory tests are analyzed by a central laboratory and include the following parameters:

Serum Chemistry:
cholesterol, phosphorus, sodium (Na ⁺), potassium (K ⁺), calcium (Ca), urea nitrogen (BUN), creatinine, albumin, total protein, aspartate transaminase (AST), alanine transaminase (ALT), alkaline phosphatase (ALP), gamma-glutamyl transferase (GGT), uric acid, total bilirubin, glucose, and lactate dehydrogenase (LDH).
Hematology:
hemoglobin, hematocrit, platelet count, red blood cell (RBC) count, MCV, MCH, MCHC, white blood cell (WBC) count, WBC differentials (%), including bands, neutrophils, lymphocytes, monocytes, eosinophils, and basophils
Urinalysis:
specific gravity, pH, glucose, blood, protein, color, nitrites, ketones, bilirubin, urobilinogen, and leukocyte esterase.

A complete physical examination is performed at screening, Weeks 4, 13, 26, 39, and at study completion (i.e., Week 52) or, if applicable, at early termination from the study. The complete examination will involve gross examination of general appearance; head, ears, eyes, nose and throat; skin; extremities; chest; abdomen; and lymph nodes. Cardiac and pulmonary auscultation and measurement of vital signs and weight will also be conducted as part of the complete physical exam. A brief physical examination, consisting of cardiac and pulmonary auscultation is performed on Day 1 prior to injection of study drug and at Weeks 8, 17, 30, and 43. Height will be recorded at screening only. Lung functioning is measured for subjects with ALS, using forced vital capacity (liter) (FVC), and in other subjects if warranted, at the discretion of the Investigator at screening, before the first injection of study drug on Day 1, at Weeks 4, 8 (as clinically warranted), and 13. Thereafter, FVC will be checked if warranted at Investigators' discretion (such as if the subject has ALS). If any of the Physical Exam findings were abnormal and clinically

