2.9 Statistical Methods

Unless specified otherwise, SAS® Version 9.4 or higher will be utilized to perform the statistical analyses of efficacy and safety measures.

Per the protocol, subjects who met all eligibility criteria were to receive single dose injections of 3,500 Units of MYOBLOC every 13 weeks (± 2 weeks) over a maximum possible duration of 1 year, for up to a total of 4 treatments via injections into the submandibular and parotid glands. Repeat injections at each treatment session were to be done when subjects returned to baseline status as determined by the Investigator, with a minimum interval of 11 weeks from the prior injection. If after the first treatment of 3,500 Units the subject developed intolerable side effects, but still wished to remain in the study, the Investigator had the discretion to decrease subsequent doses, but to no less than a total dose of 2,500 Units. Since the majority of subjects received 3500 Units, all statistical tables will present results under one treatment group labeled "Any Dose". Additionally, listings will be categorized as L = low dose (1500-2000 U); M = medium dose (2500-3000 U); H = high dose (3500 U).

Categorical variables will be summarized in general using frequencies and percentages, whereas continuous variables will be summarized in general using descriptive statistics of number of observations (n), mean, standard deviation (SD), minimum (Min), median, and maximum (Max).

In both data listings and CRF domain data tabulations, subject ID will consist of site number plus the assigned subject number.

Hypothesis testing, unless otherwise indicated, will be performed at the 5% significance level. All p-values will be rounded to four decimal places; p-values less than 0.001 will be presented as '<0.001' in all tables. All confidence intervals will be two-sided with 95% coverage.

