Abnormal findings of dental exam and oral exam will be listed, respectively, for individual subjects. Dental adverse events will be included in the analysis of adverse events.

Laboratory Assessments

For each treatment session, clinical laboratory tests of hematology, chemistry, and urinalysis (specific gravity and pH) will be summarized descriptively at available visits. Qualitative analysis of laboratory tests in terms of abnormality will be performed, using the shift-table method, for individual post-screening visits. Abnormal findings of clinical laboratory tests for individual subjects will be provided by data listing.

Pregnancy Test

Any positive findings of the pregnancy test will be listed for individual subjects.

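### SAP 5.11 ties a clinically significant laboratory abnormality to the reference range alone, and its tables give no count of subjects with a marked abnormality and no stated place for as-needed draws

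*SAP*

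**What the plan says.** SAP 5.11 plans three laboratory outputs.

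- Descriptive statistics at screening and end of session.
- A categorical table: "Qualitative findings in terms of abnormal low, normal, and abnormal high at screening and end of treatment session will be tabulated". Both this and the descriptive statistics are produced "for Treatment Session 1, Treatment Session 2, Treatment Session 4 as well as End of Study".
- A listing: "Any clinically significant abnormalities (based upon laboratory ranges) observed during the study will be listed".

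SAP 2.9.2 (Laboratory Assessments) describes the same work in broader terms. Numeric results are summarized at whatever visits have data. Abnormality is analysed "using the shift-table method, for individual post-screening visits". The listing is not limited to significant findings: "Abnormal findings of clinical laboratory tests for individual subjects will be provided by data listing".

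On sampling, SAP 2.6.2 states: "Clinical laboratory tests are conducted at screening, Weeks 13, 26, as needed", and then at study completion or early termination. Protocol 16.4.1 agrees on Weeks 13, 26 and 52 and adds: "Clinical laboratory testing will also be performed as needed". The schedules of assessments and Protocol 14.3 to 14.6 place the as-needed draws at Weeks 4, 8, 17, 30, 39 and 43. Protocol 16.4.1 also has the laboratory supply its normal values so that the upper limit of normal (ULN) is known. SAP 2.8 uses only the first record at a visit for analysis and sends repeats to the listings.

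**The concern.** The primary objective is long-term safety, and laboratory tests are a named safety measure. Three features weaken the laboratory part of the report.

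1. **The label.** Clinical significance is tied to the laboratory range and nothing else: no multiple of ULN, no grade, no size of change, and no rule that the investigator decides. A programmer could list every out-of-range value or only a judged subset, and the text does not settle which.
2. **The categories.** A value of 1.01 × ULN and one of 10 × ULN both count as high. The ULN is obtained, but the text applies it only to decide in or out of range.
3. **The time points.** The scheduled draws all fall about 13 weeks after an injection. Draws nearer to an injection, and any at Week 39, are taken only as needed. These are the draws most likely to be prompted by a clinical concern, yet 5.11 gives them no stated place in its tables.

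In addition, SAP 2.9.2 plans change scores for vital signs, weight and C-SSRS, but the text plans no numeric within-subject change for laboratory values. Once subjects leave, the means at screening and Week 52 describe different groups.

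**Working it through.** The plan contains no laboratory figure to reproduce, and SAP 2.5 states that no sample size estimation was done. The check is a comparison of the two SAP sections, followed by an illustration of what the label would mean on its literal reading.

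**Side by side**

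| Item | SAP 2.9.2 | SAP 5.11 |
|---|---|---|
| Numeric summary | any visit with data | screening and end of session |
| Abnormality table | shift at each post-screening visit | low/normal/high at screening and end of session |
| Sessions covered | each session | 1, 2, 4 and End of Study |
| Listing | all abnormal findings | clinically significant, by range |

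Each row of 5.11 is narrower than, or worded differently from, its counterpart in 2.9.2. Neither section defines a marked abnormality.

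**Illustration: chance flags if the phrase means any out-of-range value**

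Inputs:
- Ranged blood tests, from Protocol Table 3 and SAP 2.6.2: 14 hematology (8 indices and counts plus 6 differential components) + 17 chemistry = 31.
- Scheduled post-screening draws: Weeks 13, 26 and 52, so 3. Results per subject: 31 × 3 = 93.
- Subjects, for scale only: 187 (SAP 2.5; planned range 120 to 200).
- Chance out-of-range rate per test, *p*: **assumed**, 1% to 5%.

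With independent tests, P(at least one flag) = 1 − (1 − p)^m, where m = 31 for one draw and 93 for three. The expected number of flagged values is 187 × 93 × p = 17,391 × p.

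| p (assumed) | One draw | Three draws | Expected flags, 187 subjects |
|---|---|---|---|
| 1% | 1 − 0.99^31 = 26.8% | 1 − 0.99^93 = 60.7% | 174 |
| 2.5% | 1 − 0.975^31 = 54.4% | 1 − 0.975^93 = 90.5% | 435 |
| 5% | 1 − 0.95^31 = 79.6% | 1 − 0.95^93 = 99.2% | 870 |

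Blood tests are correlated, which lowers the per-subject proportions. A simulation used normally distributed values, 5% outside the range in total, equal correlation between tests, and within-subject correlation between draws of 0.6 to 0.8 (all assumed). It gave:
- inter-test correlation 0.3: about 67% at one draw and 90–94% over three;
- inter-test correlation 0.5: about 51% at one draw and 77–83% over three.

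Correlation does not alter the expected number of flags. That number does assume that every subject gives all three draws. Sessions 3 and 4 are optional and some subjects will withdraw, so the counts are upper figures for a given *p*.

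**The case against.** The case on the other side has force, and most of it limits the point.

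- **Abnormalities between scheduled visits are not lost.** The 5.11 listing covers the whole study, and 2.9.2 lists every abnormal finding by subject and plans shifts at individual post-screening visits. A reader might infer that laboratory safety is looked at only at end-of-session visits. The documents do not support that.
- **Marked values are not invisible.** SAP 2.9 includes the minimum and maximum among its standard statistics. Protocol 16.2.1 counts laboratory changes among possible adverse events, Protocol 16.2.2.1 has the investigator grade them, and SAP 5.3 summarizes severity. A reader might infer that a marked abnormality cannot be told from a trivial one, or is counted nowhere. That too goes further than the text.
- **The parenthesis is ambiguous.** It may mean significant findings among out-of-range values. The separate 2.9.2 listing of all abnormal findings makes that reading plausible.
- **Some features follow the protocol.** Session 3 is left out because no laboratory test is scheduled at Week 39, and the 13-week timing is the sampling schedule.
- **Shells are not in the text.** The SAP contents list table, listing and figure shells that were not available here. Statements about what is absent apply to the text only.

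What remains is the lack of a pre-specified summary. A maximum shows one extreme value, not how many subjects had one. Listings leave the judgement to whoever reads them after the data are known. The adverse-event route depends on what each investigator chose to record, with no stated laboratory criterion. Shift tables show category change within subjects, but not its size.

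**Conclusion.** The point holds as a worthwhile, low-cost improvement to the safety analysis, not as an error that undermines the trial. On the text available, SAP 5.11 gives no criterion for clinical significance beyond the reference range, pools slight with marked excursions, leaves as-needed draws without a stated place in its tables, and does not match SAP 2.9.2.

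The size of the labelling problem is conditional. It arises only if the phrase is read as any out-of-range value, and it then depends on an out-of-range rate and correlations that the documents do not give. Over three draws the illustration runs from about 61% of subjects (1%, independent) to 99% (5%, independent), with 77–83% at 5% and inter-test correlation 0.5. A low rate combined with correlated tests would fall below 61%. A reader might infer that most subjects are certain to be labelled with a clinically significant abnormality. The documents do not establish that. They leave it possible, and one sentence in the SAP would remove it.

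**What to change.** In SAP 5.11:

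1. Label the range-based listing *out-of-range values*, and make its scope and time points agree with SAP 2.9.2.
2. Before database lock, state a marked-abnormality threshold for each analyte as a multiple of ULN or of the lower limit of normal (LLN), for reporting only. Tabulate the number and percentage of subjects with at least one such post-screening value.
3. Add a shift from screening to each subject's lowest and highest post-screening value. Use scheduled, as-needed, repeat and early-discontinuation draws, and state this as an exception to the first-record rule in SAP 2.8.
4. Add within-subject change from screening at Weeks 13, 26 and 52.

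The cost is some SAP wording, one threshold table and a few extra output tables, all from data already collected. The downside is that worst-value shifts show more abnormalities than single-visit shifts, so the table should say that it takes each subject's extreme over all draws.

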5.12 Suicidality Assessment

For the safety population, descriptive and inferential statistics of C-SSRS will be presented at pre-injection and post-injection time points, for each of the three C-SSRS subscales (suicidal ideation, suicidal behavior, and intensity of suicidal ideation) for Treatment Session 1, Treatment Session 2, Treatment Session 3, and for Treatment Session 4. The change scores in C-SSRS subscales from pre-injection at 4 weeks, 8 weeks (first Treatment Session only), and 13 weeks post-injection were summarized descriptively.

5.13 Dental and Oral Examinations

Abnormal findings of dental and oral examination will be listed, respectively, for individual subjects.

5.14 Concomitant Medication

Concomitant medications were grouped into those taken pre-enrollment and those taken post-enrollment, based upon the starting date of both the concomitant medication and the enrollment date. Number and percent of subjects who take concomitant medications are reported for each Treatment Session. Concomitant medications will be listed, respectively, for individual subjects.

Solstice Neurosciences, LLC
SAP SN-SIAL-351

CONFIDENTIAL

22Jul2018
Page 28 of 36

